11.1.1.1 Visit 1 (Day -60 to Day -8)

The following evaluations will be performed:

- Obtain written informed consent (the specific informed consent form for pharmacogenetic and omics sampling should preferably be signed at Visit 1, but has to be signed at the latest at Visit 2 before the sample is taken).
- Record demographic data (date of signing the informed consent form, sex, race/ethnicity, age, height, and body mass index [automatically calculated in the eCRF]).
- Record medical history.
- Record CRPS history (for details, see Section 12.2.3.1).
- Record dental history (for details, see Section 12.2.3.2).
- Record physical examination outcome.
- Record body weight.
- Record vital signs.
- Record triplicate 12-lead ECG.
- Record prior/concomitant medications and therapies (dose and dosing frequency data must be recorded).
- Record adverse events.

- Take blood for safety laboratory testing.
- Collect urine for quantitative urinalysis at the central laboratory.
- Perform dipstick urinalysis.
- Perform a urine β -HCG pregnancy test.
- Perform urine drugs of abuse testing.
- Complete the assessment of the signs and symptoms of CRPS (for details, see Section 12.3.6).
- Dispense subject trial card.
- Dispense calcium and vitamin D supplements.
- Review inclusion/exclusion criteria.
- Dispense electronic diary.
- Training for electronic diary.

11.1.1.2 Baseline pain assessment phase (Day -7 to Day -1)

In order to calculate the baseline pain intensity score, subjects will be asked to rate their average CRPS-related pain intensity using an 11-point NRS once daily (in the evening) during the last 7 days prior to Visit 2, in the electronic diary. Subjects will also be asked to rate their worst and their current CRPS-related pain intensity once daily during the same period of time. The worst and average pain will be based on a 24-hour recall period.

11.1.2 Treatment Period A

Infusion visits should be separated by 3-day intervals to the extent possible (i.e., Day 1, Day 4, Day 7, and Day 10). Infusion visits on consecutive days are not allowed. The full dosing period must not exceed 21 days from the first infusion (Visit 2). To facilitate scheduling, the interval between infusion visits may be adapted, provided the 21 day time period is not exceeded and discontinuation criteria can be assessed. In case of suspension of treatment due to a suspected safety concern or a visit scheduling difficulty, resumption of treatment is allowed upon resolution of findings, with sponsor agreement.

11.1.2.1 Visit 2 (Day 1)

The following evaluations will be performed prior to the start of IMP infusion:

- Record physical examination outcome (change from Visit 1).
- Record vital signs.
- Record triplicate 12-lead ECG (at least 15 minutes prior to the start of infusion).
- Record adverse events.
- Take blood for safety laboratory testing.
- Collect urine for quantitative urinalysis at the central laboratory.
- Perform dipstick urinalysis.
- Perform semi-quantitative dipstick urinalysis for urinary ACR.
- Perform a urine β -HCG pregnancy test.

-
- Perform urine drugs of abuse testing.
 - Complete the assessment of the signs and symptoms of CRPS (for details, see Section 12.3.6).
 - Review inclusion/exclusion criteria.
 - Compliance assessment for electronic diary.
 - Check trial discontinuation criteria (for details, see Section 9.3.1).
 - Check IMP suspension criteria (for details, see Section 9.3.2).
 - Ask the subject to complete the EQ-5D-5L.
 - Ask the subject to record the average, worst, and current pain on the tablet computer at the site.
 - Measure edema, DMA, PPT, and AROM.
 - Ask the subject to complete the PROMIS-29 profile and the PROMIS-EDDEP39 (the investigator should review the subject's answer to the PROMIS EDDEP39 question before the subject leaves the site and in case of suicidal ideation the investigator should consider involvement of a mental health professional).
 - Ask the subject to complete the 6 neuropathic pain items of the SF-MPQ-2.
 - Ask the subject to complete the PCS.
 - Ask the subject to complete the PSEQ.
 - Ask the subject to complete the PGI-S.
 - Ask the subject to complete the WPAI: CRPS (US sites only).
 - Collect information for medical resources utilization and health economics (US sites only).
 - Take blood for pharmacokinetic evaluation (see Section 1.7.1 for time point).
 - Take blood for bone turnover marker evaluation.
 - Take blood for sIL-2R testing.
 - Take blood for pharmacogenetic and omics testing (see Section 11.1.1.1 for details of obtaining informed consent).

Compliance with inclusion and exclusion criteria must be confirmed before allocation to IMP. The baseline average pain intensity score must be confirmed prior to allocation by checking the electronic diary, which will provide an automatic calculation. A baseline average pain intensity score of at least 4 on the 11-point NRS is required.

A subject who has not met average baseline pain intensity requirements due to lack of compliance with the electronic diary (at least 4 average pain intensity ratings) may be rescheduled for Visit 2 (allowed only once), with appropriate re-training to ensure compliance with use of the electronic diary. Subjects who do not meet eligibility criteria due to an inadequate average pain level (less than 4 on the NRS) will be excluded from the trial.

Once the above evaluations have been performed, the subject will be allocated to IMP using the interactive response technology system and the IMP will be administered (for details, see Section 10.2).

During the infusion, a blood sample will be taken for pharmacokinetic evaluation (see Section 1.7.1 for time point).

The following evaluations will be performed after the infusion:

- Record vital signs.
- Record triplicate 12-lead ECG (at least 15 minutes after the infusion).
- Record prior/concomitant medications and therapies.
- Record adverse events.
- Take blood for pharmacokinetic evaluation (see Section 1.7.1 for time point).

11.1.2.2 Visit 3 (Day 4; ±1 day)

The following evaluations will be performed prior to the start of IMP infusion:

- Record vital signs.
- Record triplicate 12-lead ECG (at least 15 minutes prior to the start of infusion).
- Record adverse events.
- Take blood for safety laboratory testing.
- Collect urine for quantitative urinalysis at the central laboratory.
- Perform dipstick urinalysis.
- Perform semi-quantitative dipstick urinalysis for urinary ACR.
- Perform a urine β -HCG pregnancy test.
- Compliance assessment for electronic diary.
- Check trial discontinuation criteria (for details, see Section 9.3.1).
- Check IMP suspension criteria (for details, see Section 9.3.2).
- Take blood for pharmacokinetic evaluation (see Section 1.7.1 for time point).

Once the above evaluations have been performed, the IMP will be administered (for details, see Section 10.2).

The following evaluations will be performed after the infusion:

- Record vital signs.
- Record triplicate 12-lead ECG (at least 15 minutes after the infusion).
- Record concomitant medications and therapies.
- Record adverse events.
- Take blood for pharmacokinetic evaluation (see Section 1.7.1 for time point).

11.1.2.3 Visit 4 (Day 7; ±1 day)

The following evaluations will be performed prior to the start of IMP infusion:

- Record vital signs.
- Record triplicate 12-lead ECG (at least 15 minutes prior to the start of infusion).
- Record adverse events.

-
- Take blood for safety laboratory testing.
 - Collect urine for quantitative urinalysis at the central laboratory.
 - Perform dipstick urinalysis.
 - Perform semi-quantitative dipstick urinalysis for urinary ACR.
 - Perform a urine β -HCG pregnancy test.
 - Compliance assessment for electronic diary.
 - Check trial discontinuation criteria (for details, see Section 9.3.1).
 - Check IMP suspension criteria (for details, see Section 9.3.2).
 - Take blood for pharmacokinetic evaluation (see Section 1.7.1 for time point).

Once the above evaluations have been performed, the IMP will be administered (for details, see Section 10.2).

The following evaluations will be performed after the infusion:

- Record vital signs.
- Record triplicate 12-lead ECG (at least 15 minutes after the infusion).
- Record concomitant medications and therapies.
- Record adverse events.
- Take blood for pharmacokinetic evaluation (see Section 1.7.1 for time point).

11.1.2.4 Visit 5 (Day 10; ± 1 day)

The following evaluations will be performed prior to the start of IMP infusion:

- Record vital signs.
- Record triplicate 12-lead ECG (at least 15 minutes prior to the start of infusion).
- Record adverse events.
- Take blood for safety laboratory testing.
- Collect urine for quantitative urinalysis at the central laboratory.
- Perform dipstick urinalysis.
- Perform semi-quantitative dipstick urinalysis for urinary ACR.
- Perform a urine β -HCG pregnancy test.
- Compliance assessment for electronic diary.
- Check trial discontinuation criteria (for details, see Section 9.3.1).
- Check IMP suspension criteria (for details, see Section 9.3.2).
- Take blood for pharmacokinetic evaluation (see Section 1.7.1 for time point).

Once the above evaluations have been performed, the IMP will be administered (for details, see Section 10.2).

During the infusion, a blood sample will be taken for pharmacokinetic evaluation (see Section 1.7.1 for time point).

The following evaluations will be performed after the infusion:

- Record vital signs.
- Record triplicate 12-lead ECG (at least 15 minutes after the infusion).
- Record concomitant medications and therapies.
- Record adverse events.
- Take blood for pharmacokinetic evaluation (see Section 1.7.1 for time point).

11.1.3 Follow-up Period 1

In case of interruption or suspension of treatment, the first follow-up visit (Visit 6) should be scheduled at 4 days (± 2 days) after the last infusion visit. All subsequent visits must remain as originally scheduled relative to Visit 2 (e.g., Visit 7 occurs at 42 days [6 weeks] ± 3 days after Visit 2). No more than 4 infusions are allowed in Treatment Period A; any partial infusion (exceeding 20 mL) must be counted as 1 infusion.

11.1.3.1 Visit 6 (Day 15 [Week 2]; ± 2 days)

The following evaluations will be performed:

- Record vital signs.
- Record concomitant medications and therapies.
- Record adverse events.
- Take blood for safety laboratory testing.
- Collect urine for quantitative urinalysis at the central laboratory.
- Perform dipstick urinalysis.
- Compliance assessment for electronic diary.
- Check trial discontinuation criteria.
- Take blood for pharmacokinetic evaluation (at any time point during the visit).
- Take blood for bone turnover marker evaluation.

11.1.3.2 Visit 7 (Day 43 [Week 6]; ± 3 days)

The following evaluations will be performed:

- Record vital signs.
- Record concomitant medications and therapies.
- Record adverse events.
- Take blood for safety laboratory testing.
- Collect urine for quantitative urinalysis at the central laboratory.
- Perform dipstick urinalysis.
- Complete the assessment of the signs and symptoms of CRPS (for details, see Section 12.3.6).
- Compliance assessment for electronic diary.
- Check trial discontinuation criteria.

-
- Ask the subject to record the average, worst, and current pain on the tablet computer at the site.
 - Measure edema, DMA, PPT, and AROM.
 - Ask the subject to complete the PROMIS-29 profile and the PROMIS-EDDEP39 (the investigator should review the subject's answer to the PROMIS EDDEP39 question before the subject leaves the site and in case of suicidal ideation the investigator should consider involvement of a mental health professional).
 - Ask the subject to complete the 6 neuropathic pain items of the SF-MPQ-2.
 - Ask the subject to complete the PCS.
 - Ask the subject to complete the PSEQ.
 - Ask the subject to complete the PGI-S.
 - Take blood for bone turnover marker evaluation.
 - Ask the subject to complete the PGIC.

11.1.3.3 Visit 8 (Day 85 [Week 12]; +7 days)

Visit 8 must not occur prior to Day 85 in order for the subjects to have complete electronic diary data through Week 12 for the calculation of the primary endpoint.

The following evaluations will be performed:

- Record physical examination outcome (change from Visit 2).
- Record vital signs.
- Record concomitant medications and therapies.
- Record adverse events.
- Take blood for safety laboratory testing.
- Collect urine for quantitative urinalysis at the central laboratory.
- Perform dipstick urinalysis.
- Complete the assessment of the signs and symptoms of CRPS (for details, see Section 12.3.6).
- Training on electronic diary as, from Week 12, the electronic diary will ask for weekly assessments of pain intensity.
- Compliance assessment for electronic diary.
- Check trial discontinuation criteria.
- Ask the subject to record the average, worst, and current pain on the tablet computer at the site.
- Measure edema, DMA, PPT, and AROM.
- Ask the subject to complete the EQ-5D-5L.
- Ask the subject to complete the PROMIS-29 profile and the PROMIS-EDDEP39 (the investigator should review the subject's answer to the PROMIS EDDEP39 question before the subject leaves the site and in case of suicidal ideation the investigator should consider involvement of a mental health professional).

-
- Ask the subject to complete the 6 neuropathic pain items of the SF-MPQ-2.
 - Ask the subject to complete the PCS.
 - Ask the subject to complete the PSEQ.
 - Ask the subject to complete the PGI-S.
 - Ask the subject to complete the WPAI: CRPS (US sites only).
 - Collect information for medical resources utilization and health economics (US sites only).
 - Take blood for bone turnover marker evaluation.
 - Take blood for sIL-2R testing.
 - Take blood for omics testing.
 - Ask the subject to complete the PGIC.

11.1.3.4 Visit 9 (Day 113 [Week 16]; ±4 days)

The following evaluations will be performed:

- Record vital signs.
- Record concomitant medications and therapies.
- Record adverse events.
- Complete the assessment of the signs and symptoms of CRPS (for details, see Section 12.3.6).
- Compliance assessment for electronic diary.
- Check trial discontinuation criteria.
- Ask the subject to record the average, worst, and current pain on the tablet computer at the site.
- Ask the subject to complete the pain intensity question (question number 29, GLOBAL07) of the PROMIS-29 profile.
- Ask the subject to complete the PGI-S.
- Ask the subject to complete the PGIC.

11.1.3.5 Visit 10 (Day 155 [Week 22]; ±4 days)

The following evaluations will be performed:

- Record vital signs.
- Record triplicate 12-lead ECG.
- Record concomitant medications and therapies.
- Record adverse events.
- Take blood for safety laboratory testing.
- Collect urine for quantitative urinalysis at the central laboratory.
- Perform dipstick urinalysis.
- Perform a urine β -HCG pregnancy test.

-
- Complete the assessment of the signs and symptoms of CRPS (for details, see Section 12.3.6).
 - Compliance assessment for electronic diary.
 - Check trial discontinuation criteria.
 - Ask the subject to record the average, worst, and current pain on the tablet computer at the site.
 - Ask the subject to complete the pain intensity question (question number 29, GLOBAL07) of the PROMIS-29 profile.
 - Ask the subject to complete the PGI-S.
 - Take blood for bone turnover marker evaluation.
 - Ask the subject to complete the PGIC.

11.1.4 Follow-up Period 2

11.1.4.1 Visit 11 (Day 183 [Week 26]; +7 days)

Visit 11 must not occur prior to Day 183, to ensure a full 6 months of follow-up for all subjects.

If Visit 11 is not performed on Day 183, Visit 12 to Visit 15 should proceed in accordance with the originally scheduled time windows relative to Visit 11.

The following evaluations will be performed for all subjects:

- Record physical examination outcome (change from Visit 8).
- Record body weight.
- Record vital signs.
- Record concomitant medications and therapies.
- Assess further need of concomitant treatment for CRPS (in particular opioids), including decreases in dose or frequency as applicable.
- Record adverse events.
- Take blood for safety laboratory testing.
- Collect urine for quantitative urinalysis at the central laboratory.
- Perform dipstick urinalysis.
- Compliance assessment for electronic diary.
- Check trial discontinuation criteria (for details, see Section 9.3.1).
- Ask the subject to record the average, worst, and current pain on the tablet computer at the site.
- Measure edema, DMA, PPT, and AROM.
- Ask the subject to complete the EQ-5D-5L.
- Ask the subject to complete the PROMIS-29 profile and the PROMIS-EDDEP39 (the investigator should review the subject's answer to the PROMIS EDDEP39 question before the subject leaves the site and in case of suicidal ideation the investigator should consider involvement of a mental health professional).

-
- Ask the subject to complete the 6 neuropathic questions of the SF-MPQ-2.
 - Ask the subject to complete the PCS.
 - Ask the subject to complete the PSEQ.
 - Ask the subject to complete the PGI-S.
 - Ask the subject to complete the WPAI: CRPS (US sites only).
 - Collect information for medical resources utilization and health economics (US sites only).
 - Take blood for sIL-2R testing.
 - Take blood for omics testing.
 - Ask the subject to complete the PGIC.
 - Check the criteria to continue into Treatment Period B.

Decision to go into Treatment Period B

Compliance with the criteria to continue into Treatment Period B must be confirmed before allocation to IMP. The pain intensity question (question number 29, GLOBAL07) of the PROMIS-29 profile has to have a value of at least 4 at Visit 11. Subjects who do not meet the criteria to continue into Treatment Period B will continue with the Follow-up Period 2.

11.1.4.1.1 Subjects meeting the criteria to continue into Treatment Period B

For subjects continuing into Treatment Period B, the following evaluations will be performed prior to the start of IMP infusion:

- Record triplicate 12-lead ECG (at least 15 minutes prior to the start of infusion).
- Perform semi-quantitative dipstick urinalysis for urinary ACR.
- Perform a urine β -HCG pregnancy test.
- Perform urine drugs of abuse testing.
- Complete the assessment of the signs and symptoms of CRPS (for details, see Section 12.3.6).
- Check IMP suspension criteria (for details, see Section 9.3.2).
- Take blood for pharmacokinetic evaluation (see Section 1.7.2 for time point).

Once the above evaluations have been performed, the subject will be re-allocated to IMP using the interactive response technology system and the IMP will be administered (for details, see Section 10.2).

During the infusion, a blood sample will be taken for pharmacokinetic evaluation (see Section 1.7.2 for time point).

The following evaluations will be performed after the infusion:

- Record vital signs.
- Record triplicate 12-lead ECG (at least 15 minutes after the infusion).
- Record adverse events.
- Take blood for pharmacokinetic evaluation (see Section 1.7.2 for time point).

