General note: All efficacy and safety data evaluated during Treatment Period B and Follow-up Period 2 will be analyzed descriptively separately for subjects who are treated in Treatment Period B and subjects who are not treated. For subjects treated in Treatment Period B, analyses will be performed for subjects initially treated with placebo and subjects initially treated with neridronic acid.

All efficacy assessments will be evaluated for the time points indicated in the schedules of events.

To assess the efficacy of neridronic acid in subjects with CRPS

- Change from baseline in average pain intensity recorded on the tablet computer.
 - Change from Week 26 in average pain intensity recorded on the tablet computer.
 - Pain response to treatment, defined as at least 50% decrease from baseline in the average pain intensity, based on pain intensity recordings on the tablet computer.
 - Pain response to treatment, defined as at least 50% decrease from Week 26 in the average pain intensity, based on pain intensity recordings on the tablet computer.
 - Pain response to treatment, defined as at least 30% decrease from baseline in the average pain intensity, based on pain intensity recordings on the tablet computer.
 - Pain response to treatment, defined as at least 30% decrease from Week 26 in the average pain intensity, based on pain intensity recordings on the tablet computer.
 - Change from baseline in pain intensity scores determined using worst and current pain ratings recorded daily in the electronic diary.
 - Change from baseline in worst and current pain intensity ratings, recorded on the tablet computer.
 - Change from Week 26 in worst and current pain intensity ratings, recorded on the tablet computer.
 - Duration of effect based on average pain intensity recordings in the electronic diary.
 - Change from baseline in the pain intensity level of DMA.
 - Change from baseline in PPT ratios.
 - Change from baseline in the ratio of the figure of eight measurements of the affected limb versus the unaffected limb.
 - Change from baseline in the active range of motion (AROM) ratio (affected limb and unaffected limb) measured in the hand or foot, respectively.
 - Change from baseline in the CRPS Severity Score.
 - Patient Global Impression of Change (PGIC).
 - Patient Global Impression of Severity (PGI-S).
 - Change from baseline in the EuroQoL-5 Dimension-5 level (EQ-5D-5L) index score and the health-related visual analog scale (VAS) score.

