1.3.3 Criteria to continue into Treatment Period B

Safety laboratory tests will be taken at Visit 10. In case the serum calcium and/or vitamin D levels meet the exclusion criteria to continue into Treatment Period B, additional supplementation similar to the Enrollment Period is allowed between Visit 10 and Visit 11. In case of any safety laboratory retesting, the scheduling and time window of Visit 11 must not be affected.

The decision regarding whether a subject will continue into Treatment Period B will be taken at Visit 11, based on the following criteria:

- A value of at least 4 on the pain intensity question (question number 29, GLOBAL07) of the PROMIS-29 profile at Visit 11.
- The following exclusion criteria are not met:
 - Evidence of severe renal impairment (eGFR less than 30 mL/min/1.73 m² using the 2009 CKD-EPI creatinine equation [Levey et al. 2009] or a urinary ACR greater than 150 mg/g), based on central safety laboratory data obtained prior to Visit 11. A single repeat laboratory test is allowed.
 - Corrected QT interval (QTcF) greater than 470 ms (average of 3 ECGs obtained at Visit 10) according to the central ECG reading facility evaluation or QTcF greater than 470 ms at pre-dose ECG at Visit 11 according to the investigator's judgment; serum potassium outside the central laboratory's reference range at Visit 10 (a single repeat laboratory test is allowed); clinically unstable cardiac disease, including: unstable atrial fibrillation, symptomatic bradycardia, unstable congestive heart failure, active myocardial ischemia, or an indwelling pacemaker; evidence of complete left bundle branch block; complete atrioventricular block; any other known risk factor for torsade de pointes.
 - Subjects receiving medications with a known risk of torsades de pointes within 7 days prior to re-allocation.
 - Subjects taking forbidden concomitant medications/therapies or not being able to follow the rules of use of concomitant treatment (see Section 1.4.2).
 - Recent tooth extraction or other invasive dental procedure (within 3 months prior to Visit 11), unhealed or infected extraction site, or significant dental/periodontal disease (e.g., impacted molars, severe tooth decay, foci of infection) that may pre-dispose to need for tooth extraction or other invasive dental procedures during the further course of the trial.

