	Treatment Period B (only subjects meeting the criteria to continue into Treatment Period B)			Additional visits only for subjects going into Treatment Period B			
	Visit 11 ^a	Visit 12 ^b	Visit 13 ^b	Visit 14 ^b	Visit 15	Visit 16	Visit 17 ^c
Trial procedure	Day 183/ Week 26 (+7 days)	Day 186 (±1 day)	Day 189 (±1 day)	Day 192 (±1 day)	Day 197/ Week 28 (+7/-2 days)	Day 253/ Week 36 (±7 days)	Day 365/ Week 52 (+7 days)
Perform semi-quantitative dipstick urinalysis for urinary ACR	X ^s	X	X	X			
Perform a urine β-HCG pregnancy test ⁱ	X ^s	X	X	X			X
Perform urine drugs of abuse testing	X ^s						
Complete the assessment of the signs and symptoms of CRPS ^j	X ^s					X	X
Re-allocate to IMP ^k	X ^s						
Check trial discontinuation criteria	X	X	X	X	X	X	
Check IMP suspension criteria ^l	X ^s	X	X	X			
Administer IMP ^m	X ^s	X	X	X			
Ask the subject to record the average, worst, and current pain on the tablet computer at the site ^r	X ^r	X	X	X	X	X	X
Measure edema, DMA, PPT, and AROM ^t	X					X	X
Ask the subject to complete the EQ-5D-5L	X					X	X

Grünenthal
Confidential

Protocol KF7013-02 including Amendment 01

Page 28 of 172
DMS version 3.0
20 Nov 2018

	Follow-up Period 2						
	Treatment Period B (only subjects meeting the criteria to continue into Treatment Period B)				Treatment Period B		
	Visit 11 ^a	Visit 12 ^b	Visit 13 ^b	Visit 14 ^b	Visit 15	Visit 16	Visit 17 ^c
	Day 183/ Week 26 (+7 days)	Day 186 (±1 day)	Day 189 (±1 day)	Day 192 (±1 day)	Day 197/ Week 28 (+7/-2 days)	Day 253/ Week 36 (±7 days)	Day 365/ Week 52 (+7 days)
Trial procedure							
Ask the subject to complete the PROMIS-29 profile	X				X	X	X
Ask the subject to complete the PROMIS-EDDEP39	X					X	X
Ask the subject to complete the 6 neuropathic questions of the SF-MPQ-2	X				X	X	X
Ask the subject to complete the PCS	X					X	X
Ask the subject to complete the PSEQ	X					X	X
Ask the subject to complete the PGI-S	X				X	X	X
Ask the subject to complete the WPAI: CRPS ⁿ	X					X	X
Collect information for medical resources utilization and health economics ⁿ	X					X	X
Take blood for pharmacokinetic evaluation ^o	X ^s	X	X	X	X		
Take blood for sIL-2R testing	X						
Take blood for omics testing ^u	X						
Take blood for bone turnover marker					X	X	X

Grünenthal
Confidential

Protocol KF7013-02 including Amendment 01

Page 29 of 172
DMS version 3.0
20 Nov 2018

	Follow-up Period 2						
	Treatment Period B (only subjects meeting the criteria to continue into Treatment Period B)						

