- q) Compliance with the criteria to continue into Treatment Period B must be confirmed before allocation to IMP. The pain intensity question (question number 29, GLOBAL07) of the PROMIS-29 profile has to have a value of at least 4 at Visit 11. Subjects who do not meet the criteria to continue into Treatment Period B will continue with the Follow-up Period 2.
- r) Worst and average pain intensity ratings will be based on a 24-hour recall period.
- s) Only for the subjects going into Treatment Period B.
- t) Edema will only be measured in subjects reporting asymmetric edema as part of the assessment of the signs and symptoms of CRPS at baseline (Visit 2). The AROM will only be measured in subjects reporting decreased AROM as part of the assessment of the signs and symptoms of CRPS at baseline (Visit 2).

Grünenthal
ConfidentialPage 31 of 172
DMS version 3.0
20 Nov 2018Protocol KF7013-02 including Amendment 01

u) The blood sample for omics testing will be collected in consenting subjects.

v) No training needed at Visit 17.

AROM = active range of motion, β -HCG = beta-human chorionic gonadotropin, CRPS = complex regional pain syndrome, DMA = dynamic mechanical allodynia, ECG = electrocardiogram, EQ-5D-5L = EuroQol-5 Dimension-5 level, IMP = investigational medicinal product, omics = a generic term referring to analysis techniques like pharmacogenetics, genomics, epigenetics, transcriptomics, proteomics, metabolomics, PCS = Pain Catastrophizing Scale, PGIC = Patient Global Impression of Change, PGI-S = Patient Global Impression of Severity, PPT = pressure pain threshold, PROMIS-29 profile = Patient-Reported Outcomes Measurement Information System (PROMIS®)-29 profile version 2.0, PROMIS-EDDEP39 = Question EDDEP39 of the PROMIS Item Bank version 1.0 – Emotional Distress – Depression, PSEQ = Pain Self Efficacy Questionnaire, SF-MPQ-2 = Short-Form McGill Pain Questionnaire 2, sIL-2R = soluble interleukin-2 receptor, WPAL = Work Productivity and Activity Impairment.

1.8 **References**

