9.3.3 Procedure for the handling of discontinued subjects

9.3.3.1 Handling of subjects who discontinued from the trial

The principal investigator must document any discontinuation of a subject and inform the sponsor. Where applicable, the relevant IECs or IRBs must be informed with a detailed written explanation.

The following must be done for **all** discontinued subjects, including those who withdrew informed consent:

- Document the main reason for discontinuation from the trial.
- Ensure that all data collected until the time of discontinuation is transferred to the eCRF.
- Complete any other trial-related formalities, e.g., those related to discharge from the trial site.
- For subjects withdrawing consent, document in the source data the date and time of withdrawal.
- If possible, perform an Early Termination Visit, with procedures identical to Visit 17. Subjects who withdraw consent and agree to perform the Early Termination Visit must document their approval in writing.

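### The CRPS Severity Score and sign percentages are to be shown by randomized arm at Week 26, but at that visit only Treatment Period B entrants are assessed

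*Protocol*

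**What the plan says.** **Who is assessed at Visit 11.** Protocol 11.1.4.1 opens its Visit 11 list with "The following evaluations will be performed for all subjects", and CRPS signs and symptoms are not in it. They come in 11.1.4.1.1, under "For subjects continuing into Treatment Period B, the following evaluations will be performed prior to the start of IMP infusion". The schedule in Protocol 1.7.2 agrees: the Visit 11 mark in the row "Complete the assessment of the signs and symptoms of CRPS" carries footnote s, "Only for the subjects going into Treatment Period B".

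**How entrants are chosen.** The first criterion in Protocol 1.3.3 is "A value of at least 4 on the pain intensity question (question number 29, GLOBAL07) of the PROMIS-29 profile at Visit 11". Renal, cardiac, laboratory, dental and medication criteria follow.

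**What is analysed.** SAP section 4 names Weeks 12, 26 and 52 for the change in the score. It was written to the protocol of 14 March 2018. The amended Protocol 1.2 names no week and says "All efficacy assessments will be evaluated for the time points indicated in the schedules of events"; the schedule still marks Visit 11. SAP 13.3 summarises every visit with scheduled data, by visit and treatment. SAP 13.3.5 adds the score, its change from baseline, and the frequency of each sign and symptom. It makes no exception for Week 26 and sets no denominator of its own.

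**Groups and denominator.** SAP 8.1 uses two groups (placebo and neridronic acid 400 mg) for Weeks 1 to 26, ends the efficacy content of the 26-week report at Visit 11, and describes four groups, split by Period B treatment, for the final report. By default, percentages are taken over all subjects still in the trial, including those with missing values. SAP 19.1.1.7 identifies these subjects by a visit date.

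**The concern.** Treatment Period B entry depends on a pain rating taken after randomization, and an effective drug would change that rating. A Week 26 by-arm summary confined to entrants compares the part of each arm that still has pain. It does not compare the arms as randomized.

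The percentages have a second problem. A subject who attends Visit 11 but does not enter Period B counts in the denominator and cannot count as having the sign. A plot of sign proportions over time could then show a fall at Week 26 that comes from the schedule and not from the disease.

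What is at stake is how a reader of the 26-week report interprets a descriptive display at its last efficacy visit. SAP 7.1 already corrects comparable schedule gaps at Week 28 for three questionnaires, so this gap appears to have been overlooked.

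**Working it through.** The documents give no figure for this score at Week 26, so there is none to reproduce. Steps 1, 2 and 5 rest on the text; steps 3 and 4 are illustrations.

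**1. Schedule against analysis**

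| Visit | Signs and symptoms assessed in | SAP display |
|---|---|---|
| 7, 8, 9, 10 (Weeks 6 to 22) | all subjects | two randomized arms |
| 11 (Week 26) | Period B entrants only | two randomized arms |
| 16, 17 (Weeks 36, 52) | all subjects | four groups |

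There is one leak. Early Termination Visits follow Visit 17 procedures ("If possible, perform an Early Termination Visit, with procedures identical to Visit 17"), which include this assessment. SAP 19.1.1.9 re-assigns the data to the nearest visit, or to the next one if that visit has already taken place. A subject who leaves between Visits 10 and 11 can therefore supply a Visit 11 value.

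**2. Direction of the percentage error**

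Let f be the share of attendees assessed, and p_E and p_N the sign prevalence in assessed and unassessed attendees.

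- Displayed: f × p_E
- True, all attendees: f × p_E + (1 − f) × p_N
- Shortfall: (1 − f) × p_N

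The shortfall is never negative, and it is zero only if no unassessed attendee has the sign. No modelling is needed for this, apart from the Early Termination leak.

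**3. How many might be assessed**

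From Protocol 1.5.1 (Week 12): arm difference −1.0, SD of change 2.0. Assumed: both hold at Week 26; baseline mean 5.5 to 7.5 with SD 1.4; placebo change −0.5 to −1.5; change independent of baseline; safety criteria and Early Termination values ignored.

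Week 26 pain has SD √(1.4² + 2.0²) = √5.96 = 2.44. Entry is a rating that rounds to at least 4, so f = 1 − Φ(z) with z = (3.5 − mean)/2.44.

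| Baseline, placebo change | Placebo f | Active f | Gap (points) |
|---|---|---|---|
| 7.5, −0.5 | mean 7.0, z −1.43: 92.4% | mean 6.0, z −1.02: 84.7% | 7.7 |
| 6.5, −1.0 | mean 5.5, z −0.82: 79.4% | mean 4.5, z −0.41: 65.9% | 13.5 |
| 5.5, −1.5 | mean 4.0, z −0.20: 58.1% | mean 3.0, z 0.20: 41.9% | 16.2 |

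The first and last rows are the extremes of the grid. With baseline SD 1.0 to 1.8 the gap runs from 7.3 to 17.7 points. A simulation with baseline truncated to 4–10 gives 7.9 to 17.3.

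**4. Consequences under those assumptions**

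*Mean score.* With correlation ρ between score change and pain change, score-change SD σ and λ = φ(z)/(1 − Φ(z)), the difference among entrants is

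−1.0 + ρ × σ × (2.0/2.44) × (λ_active − λ_placebo).

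- Least attenuation (baseline 7.5, change −0.5, ρ 0.3, σ 2): λ is 0.279 and 0.154; −1.0 + 0.6 × 0.819 × 0.124 = −0.94.
- Most attenuation (baseline 5.5, change −1.5, ρ 0.7, σ 3): λ is 0.933 and 0.672; −1.0 + 2.1 × 0.819 × 0.260 = −0.55.
- At ρ = 0 the difference stays at −1.0.

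*Sign percentages.* The shortfall is prevalence in the unassessed × share unassessed. With equal prevalence in the unassessed of both arms:

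| Prevalence in unassessed | Case | Placebo | Active | Spurious gap |
|---|---|---|---|---|
| 0% | any | 0 | 0 | 0 |
| 20% | 7.5, −0.5 | 1.5 | 3.1 | 1.5 |
| 20% | 5.5, −1.5 | 8.4 | 11.6 | 3.2 |
| 40% | 7.5, −0.5 | 3.0 | 6.1 | 3.1 |
| 40% | 5.5, −1.5 | 16.8 | 23.2 | 6.5 |

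Entries are percentage points, with gaps taken before rounding. The order of the arms reverses if prevalence in unassessed placebo subjects exceeds that in unassessed active subjects by a factor above 2.02 (first case) or 1.39 (second case).

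**5. Final report**

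If Visit 11 is shown in the four groups, attendees in the two groups treated in Period B are all scheduled for assessment. The other two groups have essentially no Visit 11 values, and the default denominator would put their sign percentages near 0%.

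**The case against.** The strongest reply is that the plan already separates these data. Protocol 1.2 and SAP section 4 say that data from Treatment Period B and Follow-up Period 2 are analysed separately by whether the subject was retreated. Protocol 11.1.4 places Visit 11 under Follow-up Period 2, and the item stands among the procedures before the second course. On that reading the Visit 11 score is simply a pre-retreatment value.

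This does not cure the problem. Protocol 1.1.2 and SAP 5.1 run Follow-up Period 1 up until Visit 11, and SAP 8.1 assigns Week 26 to the two-arm display. Even if the separate-analysis rule is applied, the untreated groups keep the near-zero percentages.

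Much else in the reply stands:

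- The two-arm distortion belongs mainly to the 26-week report.
- Tables would show missing counts, so a careful reader could see the gap, although disclosure does not correct a percentage.
- The score is descriptive other data with no test. Tablet pain, DMA and PPT are scheduled for all subjects at Visit 11, as are edema and AROM in those with the baseline sign.
- The sizes rest almost wholly on assumptions. The −1.0 and 2.0 are Week 12 diary figures, while entry uses an item with 7-day recall. The closed form admits baselines below 4, which the inclusion criteria exclude. Ignoring the safety criteria makes the assessed shares too high.
- An edit confined to SAP 13.3.5 would conflict with SAP section 4 and with the Early Termination rule.

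Changing only the denominator would repair the percentages among those assessed. It would leave the mean score a comparison of selected subsets.

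**Conclusion.** The point holds as a low-priority correction. In the 26-week report the planned by-arm mean score at Week 26 describes a subset chosen on a post-randomization outcome. Apart from re-assigned Early Termination values, the sign percentages can only be equal to or below the all-subject value. Both statements follow from the text.

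The size does not. The figures above are illustrations, and attenuation of the mean difference requires both a drug effect on pain and a positive correlation between score change and pain change.

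A reader might infer that the bias is known to be material, that the active arm is always the more understated, or that the trial's efficacy conclusions are in doubt. The documents support none of these. The entry shares, correlation and prevalence in unassessed subjects are not given, and the order of the arms can reverse. The score lies outside the primary endpoint, the secondary endpoints and the confirmatory testing.

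**What to change.** **SAP change.** In 13.3.5 state:

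*The CRPS Severity Score and the sign and symptom percentages are not presented by randomized arm at Week 26. Week 22 (Visit 10), assessed in all subjects, is the last by-arm comparison before retreatment. Visit 11 values are summarised only as the pre-retreatment value of subjects entering Treatment Period B, by initial treatment, with assessed subjects as the denominator.*

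Matching edits:

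- SAP section 4: remove or qualify Week 26 for this score.
- SAP 7.1: record the change.
- SAP 19.1.1.9: Early Termination values re-assigned to Visit 11 are listed but not included in this summary.

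The cost is wording, plus the loss of the Week 26 by-arm display of this score.

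**Alternative, if the protocol is amended anyway.** Move the Visit 11 assessment to the all-subject list in Protocol 11.1.4.1 and remove footnote s from that schedule row. This keeps the Week 26 comparison. It costs an amendment, and an examination for 8 signs and a query on 8 symptoms for the remaining subjects at a visit they already attend.
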